20.7.3 Safety and Tolerability

The following safety and tolerability analyses will be performed:

- Incidence of AEs and SAEs will be summarized for the ITT population as well as for the Safety populations for all subjects and the 36 to 45-year-old safety subpopulation. The number and percentage of subjects with each AE and SAE will be presented in a table by MedDRA system-organ class and preferred term. Summaries will be presented by relationship to VeraCept and/or VeraCept placement or removal procedure and the severity of the adverse event. All AEs will be summarized, including these AESIs:
 - Pain during insertion
 - Pelvic infection (PID or endometritis)
 - Expulsion
 - Uterine perforation
 - Dysmenorrhea
 - Abdominal pain
- Bleeding and spotting patterns will be summarized (per Mishell [12]) for the ECYC population for the first year of treatment by the number of days in each 28-day cycle with bleeding or spotting, bleeding only and spotting only.
- The insertion pain assessed immediately after insertion will be summarized...
- Cumulative VeraCept continuation rates for Years 1 through 8 will be summarized using Kaplan-Meier methods for the Safety population. The number and percentage of subjects with each reason for discontinuation will be summarized.
- Cumulative VeraCept expulsion rates at for Years 1 through 8 will be summarized using Kaplan-Meier methods for the Safety population.

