4.1.5 Exposure Periods

The first exposure cycle starts on Day 1 of successful study drug insertion. A full exposure cycle is comprised of 28 days. One woman-year comprises thirteen 28-day cycles. The following exposure periods are defined for analysis in terms of planned study days and study cycles to facilitate the efficacy and certain safety analyses.

Exposure Period	Study Day of Period Start (PSTDY)	Study Day of Period End (PENDY)
Year 1 (Cycle 1- Cycle 13)	1	364
Year 2 (Cycle 14-Cycle 26)	365	728
Year 3 (Cycle 27-Cycle 39)	729	1092
Year 4 (Cycle 40-Cycle 52)	1093	1456
Year 5 (Cycle 53-Cycle 65)	1457	1820
First 2 Years (Cycle 1-Cycle 26)	1	728
First 3 Years (Cycle 1-Cycle 39)	1	1092
First 4 Years (Cycle 1-Cycle 52)	1	1456
5 Years (Cycle 1-Cycle 65)	1	1820

Type of Events and Study Day During an Exposure Period

ЕТҮРЕ	Event	Study Day of Event (EVTDY)		
A	Expulsion	Study Day of Expulsion date		
В	Expulsion followed by conception within 7 days	Study Day of Expulsion date		
С	Removal	Study Day of Removal date		
D	Removal followed by conception within 7 days	Study Day of Removal date		
Е	Pregnancy before expulsion	Study Day of Conception date		
F	Pregnancy before removal	Study Day of Conception date		
Н	Lost to follow-up without pregnancy, expulsion or removal	Study Day of Last Date Device in Situ.		
I	Complete period without pregnancy, expulsion or removal	Study Day of Period End Date		

Note: Removal due to partial expulsion will be treated as expulsion

Exposure Duration in Days (EXDUR):

if EVTDY-PSTDY>0 then EXDUR = min(EVTDY-PSTDY+1, PENDY-PSTDY+1); else EXDUR=.;

Exposure Duration in Cycles (NCYCF) = EXDUR/28

Number of Completed Cycles (NCYCC) = INT(NCYCF)

Number Relevant Cycles (NCYCR)

- =NCYCC+1 if last partial cycle is >=23 days
- =NCYCC+1 if last partial cycle ETYPE is B or D or E or F
- =NCYCC, otherwise.

Number of Cycles with back-up contraceptives (including emergency contraception) or no intercourse within the period or there is no diary data (NCYCEXCL):

Exclude from NCYCEXCL the cycle in which the subject had an on-treatment pregnancy (ETYPE is B, D, E, F).

Back-up contraceptives or intercourse history are recorded in subject's diary.

If there are missing values then they will be handled as follows:

Missing back-up contraceptive diary entries will be treated as no back-up contraceptive use.

Missing intercourse diary will be treated as no intercourse.

Number of Evaluable Cycles (NCYCEV) = NCYCR-NCYCEXCL

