4.1.8 Study Drug Expulsion Rate

The expulsion rate is defined as cumulative probability of device expulsion at the end of an exposure period. It is calculated as failure probability from a survival analysis.

Time variable

CYCLEN= Time to expulsion in cycles (uncompressed)

Event variable Expulsion

If ETYPE is A or B, then EXPULSION=1; else EXPULSION=0

Expulsion includes removal due to partial expulsion

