4.12.9 VeraCept Expulsion Rates

Cumulative VeraCept Expulsion Rates for Years 1 through 5 will be estimated via Kaplan-Meier method for the Safety population. The complementary log-log transformation will be used to construct 95% CIs. The subgroup analysis will also be repeated by parity status at enrollment.

VeraCept expulsion includes both total expulsion and partial expulsion. Total expulsion is defined as cases in which VeraCept is observed in the vagina, not shown in the uterus by ultrasound, or if the women confirmed expulsion. Partial expulsion cases are defined as when VeraCept is visible in the cervical canal by gynecologic exam or ultrasound. If partially expelled VeraCept is removed, the removal will be considered an expulsion event for this analysis.

- Time to expulsion in cycles will be defined as time to total expulsion discovered or removal of the partially expelled VeraCept from the date of successful insertion
- Removal of VeraCept for any other reason will be censored at the removal cycle.
- If a subject discontinued because of pregnancy, the subject will be censored at the cycle of conception
- Lost-to-follow-up will be censored at the last cycle where VeraCept is in Situ.
- Those with VeraCept still in place for protection at the end of exposure period will be censored at the end of exposure period.

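### The expulsion rate is defined as a cumulative probability but estimated as an unlabelled net rate that exceeds the share of women who expel, and an expulsion first found at pregnancy can be coded as none

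*SAP*

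**What the plan says.** SAP 4.1.8 gives the definition, "The expulsion rate is defined as cumulative probability of device expulsion at the end of an exposure period", and follows it with the estimator: "It is calculated as failure probability from a survival analysis". The event rule is "If ETYPE is A or B, then EXPULSION=1; else EXPULSION=0".

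SAP 4.12.9 names Kaplan-Meier for the Safety population, with complementary log-log intervals. Its censoring rules include "Removal of VeraCept for any other reason will be censored at the removal cycle" and "If a subject discontinued because of pregnancy, the subject will be censored at the cycle of conception". It counts a device not seen in the uterus on ultrasound as a total expulsion, and it times a total expulsion at discovery.

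SAP 4.1.5 separates type B, "Expulsion followed by conception within 7 days", timed at the expulsion date, from type E, "Pregnancy before expulsion", timed at the conception date.

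Protocol 20.7.3 extends the endpoint: "Cumulative VeraCept expulsion rates at for Years 1 through 8 will be summarized", by Kaplan-Meier, without event or censoring rules. Protocol 4.4 says that a removed or expelled device is not replaced. Neither document plans a cumulative-incidence or competing-risk estimate.

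**The concern.** A woman whose device has been removed has left the risk set for good. Censoring her makes Kaplan-Meier treat her as if she could still expel at the rate seen in women who keep the device. The failure probability then answers a hypothetical question: how many would expel if nobody had a removal, given that removals are independent of expulsion risk. A reader of the definition in SAP 4.1.8 would take the number as the share of women who expel. The two diverge as removals accumulate, and this plan expects many.

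The second issue is event coding. Protocol section 18 calls for ultrasound at pregnancy to establish whether the device is present. If it is absent and no earlier expulsion date is known, the woman can meet the SAP's definition of total expulsion, but discovery falls after conception. She becomes type E with EXPULSION=0. The expulsion is still an adverse event under Protocol 12.11 and is tabulated as an event of special interest under SAP 4.12.2, so two tables in the same report can disagree.

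Expulsion at each year is a named secondary safety endpoint, and Protocol sections 5.2 and 20 say the endpoints will be reviewed to decide on NDA filing.

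**Working it through.** **No planned figure to reproduce.** The documents state no expected expulsion rate. The attrition curve behind the illustration can be checked.

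**Attrition (SAP 3.7).** Retention is planned at 620 of 1,480 at 3 years and 350 of 1,480 at 5 years.
- (620/1,480)^(1/3) = 0.748 and (350/1,480)^(1/5) = 0.749 per year, so about 25% yearly loss. Total hazard L = -ln(0.75) = 0.2877 a year.
- Applied to all 1,605 women over 5 years: 1,605 × 13 × (1 - 0.75^5)/0.2877 = about 55,300 cycles, against a planned figure of over 54,000. The curve is consistent with the plan.

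**Expulsion hazard (assumption).** Protocol 1.1.1 reports 2% expulsion at 10 months in the second pilot phase. Held constant: h = -ln(0.98)/(10/12) = 0.0242 a year. Expulsion is part of total attrition, so other attrition is 0.2877 - 0.0242 = 0.2634 a year.

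**Competing share (assumption).** Let c be the share of other attrition that is removal rather than true loss to follow-up, with k = c × 0.2634.

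**Formulas.**
- One minus Kaplan-Meier: 1 - exp(-h t).
- Cumulative incidence: [h/(h + k)] × [1 - exp(-(h + k) t)].

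Example, Year 3 with c = 1: (0.0242/0.2877) × (1 - 0.4219) = 0.0843 × 0.5781 = 4.9%. With c = 0.25: 0.2691 × 0.2369 = 6.4%.

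| Year | One minus Kaplan-Meier | CIF, c = 0.25 | CIF, c = 0.5 | CIF, c = 1 |
|---|---|---|---|---|
| 1 | 2.4% | 2.3% | 2.2% | 2.1% |
| 3 | 7.0% | 6.4% | 5.8% | 4.9% |
| 5 | 11.4% | 9.8% | 8.4% | 6.4% |

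CIF is the cumulative incidence.

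**Sensitivity to the hazard.**
- Constant 0.01 a year: Year 5 is 4.9% against 2.7-4.1%.
- Constant 0.05 a year: Year 5 is 22.1% against 13.3-19.3%.
- Front-loaded (0.05 in Year 1, 0.015 in Years 2-3, 0.01 in Years 4-5): Year 3 is 7.7% against 6.1-7.2%, and Year 5 is 9.5% against 6.7-8.6%.

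The direction is the same throughout. The gap is smaller when expulsions come early or most attrition is loss to follow-up.

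**Simulation check.** In 28-day cycles with 1,605 women and 300 runs, all other attrition competing and a slightly higher hazard of 0.0253, the means were 7.2% against 5.1% at Year 3 and 11.8% against 6.7% at Year 5.

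**Type E coding.** Take the Phase 2 cumulative Pearl Index of 0.73 per 100 woman-years (Protocol 1.1.3), and assume that 10-50% of pregnancies have an expulsion first found at pregnancy. Mean exposure over 3 years is (1 - 0.75^3)/0.2877 = 2.01 woman-years. The omission is 0.73 × 0.10 × 2.01 = 0.15 to 0.73 × 0.50 × 2.01 = 0.73 percentage points at Year 3, which lowers the reported rate.

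**The case against.** The strongest reply is that SAP 4.1.8 gives the definition and the survival calculation in consecutive sentences, and the protocol also prescribes Kaplan-Meier. A net rate, meaning expulsion risk while the device is kept, is a legitimate target and useful for comparison with other devices. This stands. A reader might infer that Kaplan-Meier is invalid here, and the documents do not support that. What is missing is the label and the companion estimate.

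Three further inferences go too far.
- That pregnancy ends the risk of expulsion, as removal does. It does not: Protocol section 18 allows the device to stay in place until delivery, and type E exists for expulsion after conception. The competing-event argument is firm for removals only.
- That an expulsion found at pregnancy is always dated after conception. SAP 4.1.5 uses the expulsion date, the e-diary in Protocol section 13 records known or suspected expulsion daily, and the Protocol Table 1 footnotes fall back on the discovery date only when the expulsion date is unknown. A woman with an earlier date can be type A or B and counted.
- That these expulsions are hidden. They remain in the adverse event and special-interest tables.

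It is also fair that the competing share is not in the documents, and that a low share narrows the gap.

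**Conclusion.** The point holds as a mismatch between definition and estimator, plus an unreconciled coding rule. Under the stated assumptions, one minus Kaplan-Meier exceeds the cumulative incidence by about 0.6-2.1 percentage points at Year 3 (7.0% against 4.9-6.4%) and 1.7-5.0 at Year 5 (11.4% against 6.4-9.8%). The excess at Year 1 is about 0.1-0.3 points. These sizes rest on a constant pilot-derived hazard and an assumed 25-100% competing share; only the attrition comes from the plan.

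No Year 8 figure should be drawn from 25% yearly loss. Protocol 20.9 expects at least 200 of 1,605 women at 8 years, whereas 1,605 × 0.75^8 = 161, even before the assumed 10% who decline to extend.

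The type E effect is smaller and runs the other way. The two cannot be relied on to cancel, because they depend on different things. The endpoint is secondary and descriptive, and neither the Pearl Index nor the sample size is affected.

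**What to change.** (a) In SAP 4.1.8 and 4.12.9, add the Aalen-Johansen cumulative incidence of expulsion, with removal for other reasons as a competing event and loss to follow-up or end of period as censoring. Keep the Kaplan-Meier figure beside it, labelled as a net rate. If conception with the device in place is also treated as competing, state that as a convention and say whether the target is expulsion before conception or expulsion during device use.

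(b) Reconcile SAP 4.1.5, 4.1.8 and 4.12.9. Use the known or suspected expulsion date when there is one. Count an expulsion first found at pregnancy confirmation with no earlier date as EXPULSION=1, timed at the cycle of conception and taking precedence over the pregnancy censoring rule. List documented post-conception expulsions separately. State also how a type B woman who discontinued for pregnancy is handled, since the pregnancy bullet in 4.12.9 is silent on it.

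Limit the recoding to the EXPULSION variable, so that PREGNANCY and the Pearl Index do not change.

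The cost is SAP wording, one extra estimate per table and a dating convention that has to be defended, all from data already planned. The SAP is written to protocol version 3.0 and Years 1-5, so it needs revision for Years 6-8 in any case.

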4.12.10 Return to Fertility

Subjects in the safety set who desire pregnancy after having VeraCept removed will be followed for either 1 year, until they decide to no longer try to conceive, or they become pregnant, whichever comes first. The number (%) of subjects with return to fertility response will be summarized follows:

- Number of subjects who desire pregnancy after having VeraCept removed
- Number of subjects successfully contacted (b)
- Number of subjects successfully contacted but go on to use other birth control (c)
- Number of pregnancies (x)
- Pregnancy rate at the end of 1-year follow-up (%) = $100 \times \frac{x}{b-c}$

The pregnancy rate will also be calculated by parity, and by duration of use (presented by year where year = thirteen 28-day cycles) of VeraCept removal if there are more than 30 subjects at risk (b-c) in each year.

4.12.11 Vital Signs and Weight

The observed values and changes from baseline in the following vital signs and weight parameters will be summarized by visit for the Safety population:

- Systolic blood pressure (mm Hg)
- Diastolic blood pressure (mm Hg)

- Pulse rate (bpm) sitting
- Respiration rate (breaths/min)
- Body temperature
- Body weight (kg)

The number and percentage of patients reporting potentially clinically meaningful observations as defined below will be summarized by visit and treatment group:

- Systolic blood pressure: $\leq 80 \text{ mm Hg or } \geq 140 \text{ mm Hg}$
- Diastolic blood pressure: $\leq 40 \text{ mm Hg or } \geq 90 \text{ mm Hg}$
- Pulse rate: ≤ 50 bpm or ≥ 100 bpm
- Respiration rate: < 8 or > 20 breaths/min

Vital signs and weight will be included in data listings.

4.12.12 Physical Examination

Physical examination includes examination of general appearance; skin; head, eyes, ears, nose and throat; thyroid; lungs; back; breasts; heart; abdomen; extremities; and neurological system.

The number (%) of subjects with treatment-emergent abnormal (not clinically significant) and clinically significant abnormal results will be tabulated by body system by visit for the Safety population.

Physical examination results will be included in data listings.

4.12.13 Laboratory Results

All laboratory data will be presented in the listings.

p ,	Pelvic exam (string check if post IUD insertion)	X	X1	X^1		X^1	X^1	
Safety and Efficacy	Cervical cytology	X						
lfety Effic	Cervical infection tests	X ^{5,7}						
Sa	Transvaginal ultrasound ²		X^2	X^2		X^2	X^2	
	Pregnancy test-urine	X	X	X		X	X^4	
	Prior and concurrent medication	X	X	X	X	X	X	
	Adverse events		X	X	X	X	X	
	Contact IWRS	X^{13}	X ¹⁴				X	
	Measure Uterine Depth		X ⁹					
	IUD placement		X ⁹					
	IUD placement ease		X					
	IUD placement pain (11-point scale)		X ¹¹					
er	IUD removal						X	
Other	IUD removal ease						X	
	IUD removal pain (11-point scale)						X ¹²	
	Concomitant contraception		X	X	X	X	X	
	Subject education - need for contraception	X	X	X	X	X	X	
	Subject e-Diary training and re-training	X^{3a}	X X ^{3a}	X X ^{3b}	X X ^{3b}	X X ^{3b}	3v3h	
	e-Diary reviewed with subject ⁶		X ^{3a}	X30	X ³⁰	X ³⁰	X ^{3b}	Vδ
	Discontinued Subject Desiring Pregnancy							X^8

Note: The screening and enrollment visits may be combined if all protocol procedures are complete and entry criteria are met.

Footnotes

- 1. Pelvic exam for VeraCept string check by palpation or visualization
- 2. Transvaginal Ultrasound only if clinically indicated (e.g. to confirm adequate IUD placement)
- 3a. This first e-diary review, prior to VeraCept placement, to be used as training with the subject. This diary data is not part of data collection or analysis. It is intended to ensure the subject understands how to complete the diary and determine subject compliance throughout e-diary collection.
- 3b. Review for completeness. If not complete, subject to enter information, if within 7- day open timeframe. Remind the subject to complete diary contemporaneously.
- 4. Urine pregnancy test will be done at the Month 60 or exit visit and 17 days after removal/study exit by the subject at home, with a follow up call by the study coordinator or PI required to document the results.
- 5. Screening for cervical infection tests are to be done at screening unless these tests have been previously completed within 3 months of the screening visit and were negative. If a subject tests positive prior to VeraCept insertion, the subject should be treated prior to VeraCept placement. A cervical infection retest should be done 3-months post-treatment to confirm cure
- 6. Subjects will complete an e-diary through Month 60 and will receive detailed instructions on how to complete the daily e-diary. From Month 13 Month 60, only other contraceptive use and intercourse will be recorded on the e-diary by the subject.
- 7. Insertion can occur without receipt of test results if there is no clinical evidence of infection. If, after VeraCept insertion, the screening cervical infection test results are positive, the subject should be treated and retested 3 months post-treatment to confirm cure.
- 8. Subjects who prematurely discontinue from the study and are desiring pregnancy will be followed for either; 1 year, until they decide to no longer try to conceive or they become pregnant, whichever comes first. Outcome data regarding subject's ability to conceive, or the decision to no longer try to become pregnant will be collected by contacting the subject (e.g. via phone, email, etc.) and documented in the source document and eCRF.
- 9. Obtain uterine depth measurement prior to insertion
- 10. Contact subject (e.g. via phone, email, etc). Starting at Week 17 from day of VeraCept insertion.
- 11. See protocol Appendix 2 for the IUD Insertion Subject Numeric Pain Rating Scale
- 12. See protocol Appendix 3 for the IUD Removal Subject Numeric Pain Rating Scale
- 13. Upon receipt of informed consent and assent, if applicable, contact the IWRS to register the subject, initiate the subject's screening diary and obtain a subject number
- 14. Contact the IWRS to obtain an enrollment number, the IUD dispensation assignment, and initiate the enrollment diary. If an IUD insertion is a failure, contact the IWRS to record the IUD insertion failure and to obtain a second IUD dispensation assignment or to discontinue the subject.
